**PLANNED DURATION OF THE STUDY:**

Planned Start Date:	10.01.2022
Planned Completion Date:	01.08.2024

**NCT ID not yet assigned**

**Last updated: 10.01.2022**

## **Study Design and Statistical Analysis Plan**

This study was designed as a randomized, controlled, single-blind prospective clinical trial. The minimum required sample size was calculated using G\*Power Version 3.1.9.4. Assuming a confidence level of 95% (1- $\alpha$ ), a power of 80% (1- $\beta$ ), and an effect size of  $d = 0.7$ , the total required sample size for comparing three independent groups was calculated as 24, with 8 teeth in each group.

Data were analyzed using IBM SPSS Statistics Version 23 and R software. The Shapiro–Wilk test was employed to assess the normality of the data distribution. For comparisons involving three or more groups with normally distributed data, one-way analysis of variance (ANOVA) was conducted. In cases where the data did not follow a normal distribution, the Kruskal–Wallis H test was applied for comparisons across three or more groups.

Robust regression analysis was conducted to identify independent variables affecting non-normally distributed outcomes. The Fisher–Freeman–Halton test was used to examine associations between categorical variables. Inter-observer agreement was assessed using the intraclass correlation coefficient (ICC). Descriptive statistics are presented as frequencies and percentages for categorical variables; and as mean  $\pm$  standard deviation, median (minimum–maximum), or median (25th–75th percentile) for continuous variables, depending on the distribution. A p-value of  $<0.05$  was considered statistically significant.

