RESEARCH METHOD:	
The sample group for the planned study will be selected from among patients applying to the Inonu University Faculty of Dentistry Pedodontics Clinic with necrotic pulp and immature apices. Block randomization will be used to determine the material to be applied to the teeth. According to the minimum sample size determined by the power analysis, the study will be conducted on at least 24 teeth. Patients who leave the study early or do not comply with the treatment procedure will be excluded, and new patients will be added in their place. Patients will not undergo additional procedures, appointments, or radiograph requests within the scope of the study. Regeneration treatment is a popular, routinely applied procedure in our clinic and in dentistry faculties. It is also successfully performed by pedodontists and endodontists in private clinics. The protocol stipulates that each study participant will be informed about the nature of the treatment to be administered and the research to be

-------------------------	---

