conducted. Informed consent will be obtained from the patient's legal guardian. In the initial session, local anesthesia will be administered to the teeth, a rubber dam will be positioned, and the caries will be meticulously removed. Subsequently, the pulp will be meticulously eradicated through the employment of a sterile barnacle. Each canal will undergo irrigation with 20 milliliters of a 2.5% sodium hypochlorite solution. Subsequently, a volume of 20 milliliters of sterile saline will be applied to each canal. Calcium hydroxide paste will be placed as a medicament in the canals that have been dried with paper points and closed with a temporary filling. The patient will be contacted to schedule a second session between one and four weeks later. In the second session, local anesthesia will be administered without the use of a vasoconstrictor. Prior to this, a rubber dam will be placed, and the temporary filling will be removed. The calcium hydroxide paste placed in the canal as a medicament will be removed, and each canal will undergo a gentle irrigation with 20 milliliters of 17% ethylenediaminetetraacetic acid (EDTA). The canals will be dried using paper points. The induction of bleeding will be accomplished through the utilization of an excessive number of instruments, specifically a 20 number K File, which will be inserted 2 mm beyond the apical extent of the canal. Subsequently, platelet-rich fibrin or chitosan (Sigma-Aldrich) will be placed in the canal as a scaffold. In the "control group," where apical bleeding will be used directly as a scaffold, which is mentioned as the gold standard in the literature because it is the most easily accessible material, these will not be used and only bleeding from the apex will be sufficient. MTA (Angelus MTA) will be applied to the canal orifices to prevent oral fluids from leaking into the canal. The MTA will be covered with glass ionomer cement. Dental elements that are deemed suitable for endodontic restoration will undergo treatment with composite fillings. Teeth that are not amenable to restoration with composite fillings due to extensive material loss can be restored with stainless steel crowns. The protocol stipulates that patients are to be contacted for medical checkups at three-month intervals during the first year of the study, and at six-month intervals during the second year. The evaluation of the data will be conducted with the utilization of statistical software and the expertise of subject matter specialists. During the check-ups, the teeth will be evaluated according to the criteria listed below.

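### Cheap improvement, not an error: compare root length and root thickness by one prespecified ANCOVA on the pre-treatment value, at one named visit, instead of unadjusted ANOVA or Kruskal–Wallis

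*SAP*

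**What the plan says.** The SAP (Study Design and Statistical Analysis Plan) gives the method for continuous data: "For comparisons involving three or more groups with normally distributed data, one-way analysis of variance (ANOVA) was conducted". Neither this test nor its fallback takes a covariate; the fallback is Kruskal–Wallis, to be used "In cases where the data did not follow a normal distribution". The only regression is described thus: "Robust regression analysis was conducted to identify independent variables affecting non-normally distributed outcomes". It names no terms and does not mention baseline.

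The SAP names no outcome. Of the Protocol's 13 criteria (6 clinical, 7 radiographic), root length and root thickness are evidently the continuous ones. On timing, the Protocol (RESEARCH METHOD) says "During the check-ups, the teeth will be evaluated according to the criteria listed below", and check-ups are "at three-month intervals during the first year of the study, and at six-month intervals during the second year". That makes six: months 3, 6, 9, 12, 18 and 24. The end-point section aims for 12 to 18 months, which is a range and not a visit. No pre-treatment measurement of either outcome is stated.

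**The concern.** Teeth enter at different stages of root formation, so part of the spread in follow-up length and thickness was there before treatment. An unadjusted comparison of follow-up values leaves that spread in the error term. A comparison of changes removes it fully only if the slope of follow-up on baseline is one. With 8 teeth per arm the choice affects precision, and the plan does not make it. The Protocol's rationale, that roots go on developing after treatment, makes change a plausible reading, but nothing fixes it.

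What is at stake is precision on two secondary-looking measurements and a clear statement of what is tested. The comparison of success rates is not affected.

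**Working it through.** **Inputs.** From the documents: 24 teeth, 8 per arm, α = 0.05 and effect size 0.7 (SAP); effect size 0.25 (Protocol, POWER ANALYSIS). Assumed, because not given: correlation r between baseline and follow-up, equal SDs, a common linear slope, equally spaced means, and one value per independent tooth.

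**1. The plan's own figure.** For one-way ANOVA the noncentrality is λ = N·f², with 2 and N − 3 df. With f = 0.7, N = 21 gives 75.4% power. N = 24 (λ = 24 × 0.49 = 11.76) gives 82.2%. So the SAP's 24 at 80% is reproduced if its 0.7, labelled d, is read as Cohen's f. With f = 0.25, λ = 24 × 0.0625 = 1.5 and power is 16.0%. The disagreement between the two documents on effect size is a separate matter.

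**2. Variance of a difference between two arms, relative to follow-up values.**
- Follow-up values: 1
- Change: 2(1 − r)
- ANCOVA: (1 − r²) × 20/19, where 20/19 = 1 + 1/19 is the expected cost of estimating the slope from 21 within-arm df

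ANCOVA is no worse than follow-up values when (1 − r²) × 20/19 ≤ 1, so r² ≥ 1/20 and r ≥ 0.22. It is no worse than change when (1 + r) × 20/19 ≤ 2, so r ≤ 0.90. At r = 0 its variance is 1.05 against 1 for follow-up values. At r = 0.95 it is 0.103 against 0.100 for change.

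**3. Power.** Divide λ by the relative variance; df are 2, 21 for ANOVA and 2, 20 for ANCOVA. Example: f = 0.7, r = 0.5, ANCOVA: 11.76 / (0.75 × 20/19) = 14.9, giving 90%.

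| f | r | Follow-up | Change | ANCOVA |
|---|---|---|---|---|
| 0.7 | 0 | 82% | 51% | 80% |
| 0.7 | 0.3 | 82% | 67% | 84% |
| 0.7 | 0.5 | 82% | 82% | 90% |
| 0.7 | 0.7 | 82% | 97% | 98% |
| 0.25 | 0 | 16% | 10% | 15% |
| 0.25 | 0.5 | 16% | 16% | 19% |
| 0.25 | 0.7 | 16% | 24% | 26% |
| 0.25 | 0.9 | 16% | 62% | 62% |
| 0.25 | 0.95 | 16% | 91% | 90% |

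Simulation agrees. Type I error is about 5% for all three methods at every r from 0 to 0.95.

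**4. Interval width.** The mean 95% CI half-width for one scaffold against blood clot, in follow-up SDs, at r = 0.3, 0.5, 0.7, 0.9 is:
- Follow-up: 1.03 throughout
- Change: 1.22, 1.03, 0.80, 0.46
- ANCOVA: 1.01, 0.91, 0.75, 0.46

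**5. Unequal SDs** (f = 0.25; r = 0.7, 0.8, 0.9). ANCOVA does not depend on the baseline scale and stays at about 26, 36, 62%. Change gives 19, 26, 43% if the follow-up SD is 0.8 times the baseline SD, and 27, 38, 64% if it is 1.2 times.

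**6. Chance imbalance.** The baseline difference between two arms of 8 has SD √(2/8) = 0.5. A given pair therefore differs by more than 0.5 SD with probability P(|Z| > 1) = 32%. For at least one of the three pairs it is 58% (simulated). Given a 0.5 SD gap, the follow-up comparison shifts by 0.5r and the change comparison by 0.5(1 − r) the other way. At r = 0.7 these are 0.35 and 0.15 SD. The ANCOVA shift is zero.

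**The case against.** **The gain is small on the likeliest reading.** If change is intended and r is high, ANCOVA adds little: about 0 to 2 points at r = 0.7 to 0.9 for the two effect sizes in the documents. It loses about 1 point at r = 0.95, and about 2 points if the follow-up SD exceeds the baseline SD. This stands. Between those effect sizes the gain can be somewhat larger (44% against 48% at f = 0.35, r = 0.7). The large gains are over follow-up values at high r and over change at low r. Since r is unknown, the case for ANCOVA is that it stays close to the better option throughout.

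**The baseline image may not be usable.** This also stands. Its existence is inferred from selecting patients "with necrotic pulp and immature apices". The Protocol adds: "Patients will not undergo additional procedures, appointments, or radiograph requests within the scope of the study". Nothing shows that routine images are standardised. If they are not, r and the gain fall.

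**Stronger readings that the documents do not support.**
- A reader might infer from the imbalance figures that the planned tests are biased. They are not. The shifts are conditional on a gap and average out over randomisations, and type I error is about 5%.
- A reader might infer that both follow-up and change will be tested and the better one reported. That would put the false-positive chance at about 9 to 10%, but neither document says it will be done.
- A reader might want a permutation p-value within blocks, since "Block randomization will be used to determine the material to be applied to the teeth". Block size is not given, nor whether replacement patients keep the block. With assumed blocks of 3, that test loses up to about 4 points to change scores at high r (58% against 62% at f = 0.25, r = 0.9). It is not recommended here.

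**The robust regression sentence** might be read as baseline adjustment. It covers only non-normal outcomes and names no variables, so it does not fill the gap.

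**Conclusion.** The planned tests are valid, and a better method is available at small cost. For r of about 0.22 to 0.90, one ANCOVA is at least as precise as either unadjusted analysis. At f = 0.7 and r = 0.5 it raises power from 82% to 90% against both. Outside that range its worst loss with equal SDs is about 5% in variance, or about 2 points of power.

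The result rests on an assumed r, a linear relation, roughly normal data, one value per independent tooth and a usable pre-treatment image. It is a point to consider, held with medium confidence. Naming the variable and the visit is needed whichever method is used.

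**What to change.** 1. State that root length and root thickness are measured on the existing pre-treatment radiograph, by the same method and on the same root or roots as at follow-up, with one rule giving one value per tooth. Request no extra radiograph.
2. For each outcome, replace the ANOVA/Kruskal–Wallis pair with one prespecified ANCOVA: value at one visit named in advance = scaffold group + pre-treatment value. Month 12 is an example; it is on the schedule and opens the 12-to-18-month goal.
3. Report adjusted differences from blood clot with 95% CIs from that same model. Label change scores and other visits descriptive.
4. If no usable pre-treatment image exists, the adjustment cannot be made. Still name one variable and one visit.

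The success-rate comparison stays as it is.

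Cost: SAP wording, reading about 24 existing images for two outcomes, and one degree of freedom. The possible power loss is up to about 2 points against follow-up values near r = 0, about 1 point against change at r = 0.95, and about 2 points against change if the follow-up SD is the larger.

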
**A- CLINICAL**

1. Loss of Tooth
2. Presence of pain

	
 
3. Percussion and Palpation Sensitivity
 
4. Presence of Pathological Mobility
 
5. Presence of fistula
 
6. Evaluation of restoration
 
 
B- RADIOGRAPHIC
 
 
1. Pulp Obliteration
 
2. Internal - External Root Resorption
 
3. Apical Radiolucency
 
4. Increase - Decrease in Lamina Dura Width
 
5. Presence of Ankylosis
 
6. Root length
 
7. Root thickness
 

--	--

POWER ANALYSIS:	
The number of people in the study was decided by a calculation called "power analysis." The G*power 3.1 program was used to calculate the sample size. The sample size was determined to be 24, with 8 teeth for each group. The effect size was set at 0.25, the margin of error at 0.05, the confidence level at 0.95, and the universe representation power at 0.95 Cohen states that the sample size for which power values ranging from 0.90 to 0.99 were calculated should be reached (5).
 
5. Cohen, J, (1988), Statistical Power Analysis for the behavioral sciences, 2. Edition, Taylor & Francis INC, New York, US.)

------------------------	--

END POINT OF THE RESEARCH	
The goal of this study is to follow patients over time to see if regeneration treatment works for molar teeth with open apex. We will use three different scaffolds for the treatment. No clinical controlled study has been found in the literature on regeneration with molar teeth. The existing data are in the form of case reports or studies performed on incisors. The goal of the study is to successfully obtain 12-18 months of clinical and radiographic follow-up with at least 24 teeth. We will compare the success rates of the materials used based on the data we get. Since scientists haven't found the perfect material yet, this study will be a big help to researchers when it's finished.

----------------------------------	---

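### Teeth are examined at up to six check-ups with unequal follow-up, but the SAP's group tests treat observations as independent and name no analysis visit; root length and thickness need one mixed model on all films

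*SAP*

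**What the plan says.** The protocol's RESEARCH METHOD section calls patients back "at three-month intervals during the first year of the study, and at six-month intervals during the second year". It adds: "During the check-ups, the teeth will be evaluated according to the criteria listed below". The list that follows has six clinical and seven radiographic criteria, and root length and root thickness are among the latter. END POINT OF THE RESEARCH sets the target as to "successfully obtain 12-18 months of clinical and radiographic follow-up with at least 24 teeth". RESEARCH METHOD also says that patients who leave early or do not comply are excluded and replaced.

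The SAP (Study Design and Statistical Analysis Plan) compares the arms as follows. For normally distributed data, "one-way analysis of variance (ANOVA) was conducted"; otherwise, "the Kruskal–Wallis H test was applied for comparisons across three or more groups". Categorical criteria go to the Fisher–Freeman–Halton test. On regression it says only: "Robust regression analysis was conducted to identify independent variables affecting non-normally distributed outcomes". No visit term or tooth effect is stated for that regression. The intraclass correlation is for agreement between observers, not between visits. The SAP names no analysis visit, no repeated-measures method and no rule for a missed visit.

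**The concern.** The design is longitudinal and the group tests are not. One-way ANOVA and Kruskal–Wallis need independent observations, so a tooth can enter a given test only once. With follow-up of 12 months for some teeth and 18 for others, the analyst has three routes:

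- drop the teeth that have not reached the later visit;
- pool 12-month and 18-month values in one test;
- run a separate test at each visit, without using the correlation between visits on the same tooth.

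The plan does not choose among them. With 8 teeth per arm, each tooth dropped is 1/8 = 12.5% of an arm. Pooling adds noise, and adds bias if the mix of follow-up lengths differs between arms. Separate tests multiply the chances of a false positive and leave open which result counts.

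**Working it through.** **1. Visits.** Year 1: 12/3 = 4. Year 2: 12/6 = 2. Total 6, at months 3, 6, 9, 12, 18 and 24.

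**2. Follow-up that the calendar allows.** PLANNED DURATION OF THE STUDY gives 10.01.2022 to 01.08.2024. Read as day.month.year, this is about 30.7 months. Only teeth treated in the first 30.7 − 24 = 6.7 months can reach month 24, and only those treated in the first 30.7 − 18 = 12.7 months can reach month 18. Unequal follow-up is therefore likely as well as permitted.

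**3. The plan's own sample size.** One-way ANOVA, noncentral F with λ = N·f² and 2 and N − 3 degrees of freedom. The SAP's 0.7 is labelled d; read as Cohen's f, N = 24 gives λ = 24 × 0.49 = 11.76 and power 0.822. N = 21 gives 0.754. So 24 reproduces for 80% power, as a calculation with one value per tooth. (The protocol's POWER ANALYSIS section reaches 24 from different inputs; that is a separate matter.)

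**4. Cost of each route.**

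- Dropping: 22 teeth left gives power 0.779, and 18 left gives 0.668.
- Pooling: at an assumed growth of 0.05–0.10 mm per month, a 12-month value placed among 18-month values is off by 6 × 0.05 = 0.3 mm to 6 × 0.10 = 0.6 mm.
- Separate tests: if independent, six tests at 0.05 on one outcome have a familywise error of 1 − 0.95⁶ = 0.265. Visits on the same tooth are correlated, so 0.265 is an upper figure.

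**5. Gain from using all films.** The documents give no SDs. Assumed for root length: SD of 18-month growth g = 0.4–0.8 mm, reading-error SD e = 0.3–0.6 mm, between-tooth baseline SD 2 mm, linear growth, and a baseline film.

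- Month-18 change, variance per tooth: g² + 2e².
- Model-based 18-month growth, variance per tooth: g² + e²/S, where S is the sum of squared deviations of t/18 from its mean. For films at 0, 3, 6, 9, 12 and 18 months, S = 0.648. For a tooth stopping at month 12, S = 0.278.
- Example, g = 0.4 and e = 0.3: change = 0.16 + 0.18 = 0.340; model = 0.16 + 0.09/0.648 = 0.299; ratio 0.88.
- Same SDs with 2 of 8 teeth per arm stopping at month 12: a stopped tooth has 0.16 + 0.09/0.278 = 0.484. The variance of the arm difference is 2/(6/0.299 + 2/0.484) = 0.0826 with the model, against 2 × 0.340/6 = 0.1133 with the change score on 6 teeth; ratio 0.73.

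| g, e (mm) | Variance ratio, complete | Variance ratio, 2 of 8 lack month 18 |
|---|---|---|
| 0.4, 0.3 | 0.88 | 0.73 |
| 0.4, 0.6 | 0.81 | 0.70 |
| 0.8, 0.3 | 0.95 | 0.75 |
| 0.8, 0.6 | 0.88 | 0.73 |

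The reductions are 5–19% and 25–30%. With films only at 0, 6, 12 and 18 months they are 2–8% and 20–22%.

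**6. Baseline must be handled.** A mixed model with a free arm term that reports the arm difference in root length at month 18 carries the baseline spread. Under the same assumptions its variance per tooth is 4.22 mm² against 0.34 mm² for the change score at g = 0.4, e = 0.3. Over the whole range it is 3.6 to 12.4 times that of the change score. The gain in step 5 belongs to the growth contrast only.

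**The case against.** A reader might infer that the repeated measurements go unused, or that one visit has been chosen and every tooth missing it is lost. The documents say neither. No visit is named; tests at every visit or on change from baseline would fit the SAP's text, and the robust regression could carry a visit term. What stands is that the SAP leaves the choice open and states no method that uses the correlation within a tooth.

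Replacing early leavers may restore the number of teeth, which weakens the scenario of two lost teeth per arm. It does not deal with a single missed visit or with a tooth treated too late to reach month 18, and it discards the earlier visits of the tooth replaced.

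The gain also depends on films being taken. RESEARCH METHOD says that no extra radiographs will be requested for the study, so a film at every check-up is not assured. With complete data and films only at 0, 12 and 18 months the gain is 1–3%. This objection stands: with few films and full follow-up, the case rests on handling unequal follow-up rather than on precision.

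Finally, growth may slow. If mean growth follows 1 − exp(−t/τ) with an assumed τ of 6–12 months, a straight line puts fitted month-18 growth 10–16% too high. A random-slope model on 24 teeth may also fail to converge. Both points stand and are the reason for a stated fallback.

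**Conclusion.** The point holds as a recommended change; it does not make the trial invalid. The mismatch between a six-visit schedule with 12 to 18 months of accepted follow-up and group tests for independent observations is plain from the documents. The size of the gain is not, because it rests on assumed SDs, linear growth and the films actually taken. It is modest when data are complete and substantial when follow-up is unequal, which the calendar makes likely. The figures are for root length; none were worked for thickness. The other 11 of the 13 criteria, and so most of the success-rate comparison, lie outside this point.

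**What to change.** For root length and root thickness, make the main analysis one linear mixed model per outcome on all available films:

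- Handle baseline either by modelling change from baseline with the baseline value as covariate, or by constraining the arms to a common baseline mean.
- Include time, arm-by-time and a tooth-level random effect (slope as well as intercept where it can be fitted), with Kenward–Roger degrees of freedom.
- Report the arm difference in growth at one month stated in advance.
- Plot the course. If it is not linear, or the random-slope model does not converge, use categorical visit with a random intercept.
- Keep the single-visit change-score ANOVA as a sensitivity analysis.

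The cost is SAP wording and slightly more analysis, in R, which the SAP already names. No visits, films or patients are added. The downside is an assumption about the time course. The categorical criteria would need their own statement of visit and method.

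### Robust regression is used to identify predictors at p<0.05, only for outcomes judged non-normal, in a trial planned for at least 24 teeth, and is not labelled exploratory

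*SAP*

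**What the plan says.** The relevant text is in the SAP, Study Design and Statistical Analysis Plan. On regression it has one sentence: "Robust regression analysis was conducted to identify independent variables affecting non-normally distributed outcomes". It lists no candidate variables, outcomes, visit, estimator or method for standard errors.

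Normality is handled just before this: "The Shapiro–Wilk test was employed to assess the normality of the data distribution". For data judged normal, only a group comparison is named: "For comparisons involving three or more groups with normally distributed data, one-way analysis of variance (ANOVA) was conducted". Kruskal-Wallis takes its place otherwise. Regression is mentioned only on the non-normal side.

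The section ends with one rule for every test: "A p-value of $<0.05$ was considered statistically significant". No adjustment for multiple testing is stated.

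On size, the SAP says "the total required sample size for comparing three independent groups was calculated as 24, with 8 teeth in each group" and calls this a minimum. The protocol agrees under Research Method: "the study will be conducted on at least 24 teeth". The protocol does not mention the regression, so nothing there narrows it.

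**The concern.** Two features of the sentence cause trouble, and naming the covariates would cure neither.

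First, the stated purpose is to find variables that affect an outcome, and the only criterion in the plan is the p<0.05 that also governs the scaffold comparison. Several coefficients tested this way in about 24 teeth give a material chance that at least one is declared a predictor by luck. Usual robust-regression standard errors are large-sample approximations, and with few teeth per model term they can be too small, which adds to the error. A scaffold term in a large model of this kind would be affected too.

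Second, a normality test decides whether predictors are examined at all. With few teeth its result for a moderately skewed outcome is close to a coin toss. Root length might get a regression and root thickness none, for reasons unrelated to the clinical question.

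At stake is a report that names factors as affecting root development when some are chance findings, and that treats two parallel outcomes differently without a reason.

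**Working it through.** **Inputs from the SAP.** Minimum 24 teeth, 8 in each of 3 groups; threshold 0.05; Shapiro-Wilk for normality; regression named for non-normal outcomes only. **Assumed, because the SAP does not say:** 3, 5 or 8 model terms, two of them the scaffold indicators; M-estimation (Huber or Tukey biweight) with asymptotic standard errors; all true effects zero.

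**1. The plan's own figure.** For one-way ANOVA, power comes from the noncentral F with λ = N·f². Reading the SAP's 0.7 as Cohen's f, N = 24 gives λ = 24 × 0.49 = 11.76 on 2 and 21 degrees of freedom and power 0.822; N = 21 gives 0.754. So 24 is reproduced for 80% power on that reading. That calculation concerns a three-group comparison and makes no provision for a regression with further terms.

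**2. Terms against teeth.** Residual degrees of freedom are 24 − p − 1: 20, 18 and 15 for p = 3, 5 and 8.

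**3. At least one false predictor, per outcome.** If each test held exactly 5% and the tests were independent, the chance would be 1 − 0.95^p. The last column is from simulation at n = 24 under the null (two scaffold indicators plus 1, 3 or 6 null covariates).

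| Terms p | 1 − 0.95^p | Simulated, Huber and Tukey |
|---|---|---|
| 3 | 14% | 14-20% |
| 5 | 23% | 22-29% |
| 8 | 34% | 36-51% |

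A separate simulation with Tukey's biweight only, over normal, gamma (shape 2), lognormal and t(3) outcomes, gave 13-22%, 26-36% and 45-54%. The upper ends come from a normal instead of a t reference. Most of the error is therefore plain multiplicity; the standard errors add to it mainly when there are many terms.

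**4. Error per coefficient.** With scaffold plus 1 to 6 covariates, the rate was about 6-8% for Huber and 7-15% for Tukey. In the smallest models (t reference), Huber gave 4.4-5.9% with one predictor and 5.1-6.4% with two; Tukey gave 6.9% and 5.8-7.0%.

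**5. Scaffold within such a model.** The joint 2-degree-of-freedom scaffold test rejected under the null in 7-10% of runs with 3 added covariates, 7-16% with 5 and 11-29% with 8 (5, 7 and 10 terms in all).

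**6. The normality gate.** If Shapiro-Wilk rejects with probability q, two independent outcomes of the same shape are treated differently with probability 2q(1 − q). At n = 24:

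| Outcome shape | q | 2q(1 − q) |
|---|---|---|
| Gamma, shape 2 | 0.622 | 2 × 0.622 × 0.378 = 0.47 |
| t(3) | 0.386 | 2 × 0.386 × 0.614 = 0.47 |
| Normal | 0.054 | 2 × 0.054 × 0.946 = 0.10 |
| Lognormal | 0.969 | 2 × 0.969 × 0.031 = 0.06 |

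The SAP does not say whether the test is applied to pooled data, by group or to residuals. If it is applied by group (n = 8) and any rejection counts, gamma (shape 2) gives q = 1 − (1 − 0.186)³ = 0.461 and a split of 2 × 0.461 × 0.539 = 0.50. Root length and thickness come from the same teeth; if they are correlated, the split would be less frequent than under independence.

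**The case against.** The strongest case against is that the SAP describes no search. It gives no candidate list, screening step or selection rule, and its wording is also common for fitting one model and reading the coefficients. The p<0.05 line is general, not written for the regression. All of that is fair. But it is the only criterion given, and reading several coefficients of one model against it produces the error in step 3 without any selection procedure.

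Several stronger readings are tempting, and the documents do not support them.

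- **That a false predictor is more likely than not.** This depends on a predictor count the SAP does not give. With 3 terms the chance is 14-20%; it reaches about one half only near 8 terms with Tukey's biweight. More outcomes or visits would raise it, but the SAP does not say how many would be modelled.
- **That even a single coefficient is tested above 5%.** Small Huber models are at or near nominal (step 4), and the estimator is unstated. A bootstrap could behave differently.
- **That the trial's scaffold comparison is compromised.** The SAP gives group comparisons to ANOVA, Kruskal-Wallis and Fisher-Freeman-Halton, and does not say that scaffold enters the regression. Step 5 applies only if it does.
- **That regression is ruled out for normal outcomes.** The SAP is silent there; it does not forbid it. Root length and root thickness are illustrations, since no outcome is named for the regression.

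Finally, 24 is a minimum, and with more teeth the standard-error problem shrinks. The multiplicity does not.

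**Conclusion.** The concern holds in limited form. The SAP plans to identify predictors at a general p<0.05, for non-normal outcomes only, in a trial sized at a minimum of 24 teeth, and does not call this exploratory. The chance of at least one false predictor per outcome is roughly 14-20%, 22-29% or 36-51% for 3, 5 or 8 null terms. Those figures rest on an assumed number of terms and on M-estimation with asymptotic standard errors. Inflation per coefficient is slight for small Huber models and clear for Tukey's biweight or many terms. Harm to a scaffold p-value is conditional on scaffold being in a large model. The gate is the part least dependent on those assumptions: for moderately skewed outcomes it can treat two alike outcomes differently nearly half the time, though hardly ever for strongly skewed ones. The plan should be changed, because the change is cheap and removes both problems.

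**What to change.** Replace the regression sentence with one prespecified model, used for both root length and root thickness whatever the Shapiro-Wilk result:

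- **Model.** The value at one named follow-up visit, on scaffold plus the pre-treatment value of the same measure. The pre-treatment value is assumed to be available from the treatment radiograph; the protocol rules out extra radiographs for the study.
- **Scaffold p-value.** By permutation of allocation within the randomization blocks, since the protocol specifies block randomization. This needs the block of every tooth on record, including teeth added as replacements.
- **Standing.** State that this model is the scaffold comparison for these two outcomes, in place of ANOVA/Kruskal-Wallis, so that each outcome does not end with two scaffold p-values and no order between them.
- **Other factors.** Report as exploratory estimates with confidence intervals, and make no claim that predictors were identified. Suppressing their p-values altogether is not needed once the label is clear.

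The cost is a few lines of SAP text and a short permutation script in R, which the SAP already names. The downside is small: no confirmatory claims about other predictors.
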